#### 6.1.2.1. Main Analysis

- Estimand strategy: Treatment policy (Section 2.2.1.1.2).
- Intercurrent events and missing data: All data collected are included.
- Analysis set: Safety population (Section 4).
- Analysis timing: At primary analyses (when all primary endpoint data are available).
- Analysis methodology: 95% CIs of the proportion of participants reporting those events will use the Clopper-Pearson method (Section 5.2.1).
- Descriptive statistics, including the proportion (%), the numerator (n) and the denominator (N) used in the proportion calculation, and the 95% CI for percentage using the Clopper-Pearson method, will be presented for each vaccine group for each analysis interval (Section 5.2.1).
- Bar charts with the proportions of participants for each variable within the specified interval will be plotted for each group. The bars may be divided into relatedness categories to highlight the proportions of participants with related events.
- The main analysis will be based on AEs and will exclude the reactogenicity events that were reported in the AE CRF (except for SAEs) (Section 3.1.1.3).

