3. OBJECTIVES, ENDPOINTS, AND ESTIMANDS

Objectives	Endpoints	Estimands
Primary:	Primary:	Primary:
To describe the safety and tolerability of RSVpreF at each dose level in children 5 to <18 years of age and children 2 to <5 years of age.	Prompted local reactions (pain at the injection site, redness, and swelling). Prompted systemic events (fever, vomiting, diarrhea, headache, fatigue/tiredness, muscle pain, and joint pain). AEs. SAEs. NDCMCs.	In participants receiving 1 dose of study intervention at each dose level, for each age stratum: The percentage of participants reporting local reactions within 7 days after vaccination. The percentage of participants reporting systemic events within 7 days after vaccination. The percentage of participants reporting systemic events within 7 days after vaccination. The percentage of participants reporting AEs from vaccination through 1 month after vaccination. The percentage of participants reporting SAEs throughout the study.
		The percentage of participants reporting NDCMCs throughout the study.

Objectives	Endpoints	Estimands
Secondary:	Secondary:	Secondary:
To describe the immune response elicited by RSVpreF at each dose level in children 5 to <18 years of age and children 2 to <5 years of age.	RSV A and RSV B NTs.	 In participants in compliance with the key protocol criteria (evaluable immunogenicity population): GMTs of NT for RSV A and RSV B 1 month after vaccination. GMTs of NT for RSV A and RSV B before vaccination. GMFRs of NT for RSV A and RSV B from before vaccination to 1 month after vaccination.
To describe the cell-mediated immune response in children 5 to <18 years of age and children 2 to <5 years of age.	RSV F antigen–specific CD4+ T cells secreting IFNγ. RSV F antigen–specific CD4+ T cells secreting IL-4.	In participants in compliance with the key protocol criteria (evaluable immunogenicity population): • Median frequencies of RSV F antigen—specific CD4+ T cells expressing IFNy before vaccination and 1 month after vaccination. • Median frequencies of RSV F antigen—specific CD4+ T cells expressing IL-4 before vaccination and 1 month after vaccination.

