9. STATISTICAL CONSIDERATIONS

Methodology for summary and statistical analyses of the data collected in this study is described here and further detailed in the SAP, which will be maintained by the sponsor. The SAP may modify what is outlined in the protocol where appropriate; however, any major modifications of the primary endpoint definitions or their analyses will also be reflected in a protocol amendment.

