9.3.2. Primary Endpoint(s)/Estimand(s) Analysis

Table 5. Primary Endpoint Analyses

Endpoint	Statistical Analysis Methods
Safety	 Descriptive statistics will be provided for each reactogenicity endpoint for each RSVpreF dose level within each age stratum. Local reactions (redness, swelling, and pain at the injection site) and systemic events (fever, fatigue/tiredness, headache, vomiting, diarrhea, muscle pain, and joint pain) from Day 1 through Day 7 after vaccination will be presented by maximum severity and any severity. Descriptive summary statistics will include counts and percentages of participants with the indicated endpoint and the associated Clopper-Pearson 95% CI (Section 9.3.1.1). AEs and SAEs will be categorized according to MedDRA terms. All of the AEs within 1 month and SAEs/NDCMCs throughout the study will be descriptively summarized with counts, percentages, and associated Clopper-Pearson 95% CIs for each RSVpreF dose level within each age stratum (Section 9.3.1.1). Descriptive summaries may also be provided for the combined age group (2 to <18 years) within the same RSVpreF dose level.

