## 2.1. Modifications to the Analysis Plan Described in the Protocol

There is no change in analysis from the plan specified in the protocol.

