## 2.2.1.1.2. **AE Estimands**

AE estimands have the same attributes (treatment condition, population, intercurrent events, population-level summary) as reactogenicity estimands (Section 2.2.1.1.1), except:

• Variables: AEs reported within 1 month after vaccination (Section 3.1.1.3).

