#### 3.1.1.3. Adverse Events and Serious Adverse Events

Standard algorithms for handling missing AE dates and missing AE severity will be applied as described in the Pfizer vaccine data standard rules. Completely missing AE start dates will not be imputed.

The following derivations will be included for each participant:

- 1. Any AE reported within 1 month after vaccination If the AE started on the same day of vaccination, if the AE start time is before the vaccination time, this AE would not be counted. Otherwise, if the AE start time is missing or after the vaccination time, the AE is included. Any AE reported after the 1-month visit will not be included in the analysis.
- 2. Any related AE reported within 1 month after vaccination Similar to above except only a related AE is included (but excluding related reactogenicity reported within 7 days of vaccination) (Section 3.1.1).
- 3. Any immediate AE (AE start time is within 30 minutes after vaccination) reported after vaccination Only include AEs that started on the same day of vaccination and with nonmissing AE start time that is within 30 minutes of vaccination. If the immediate AE is a related reactogenicity event, this would not be included as an immediate AE.
- 4. Any severe AE reported within 1 month after vaccination.
- 5. Any life-threatening AE reported within 1 month after vaccination.
- 6. Any AE leading to study withdrawal after vaccination.
- 7. Any SAE reported throughout the study.
- 8. Any NDCMC reported throughout the study.
- 9. Any AESI reported throughout the study.

Variables 1 through 6 listed above will be derived from excluding any reactogenicity (but not excluding reactogenicity SAEs) reported in the AE CRF during the e-diary collection period. AESIs are flagged in the CRF.

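### The SAP's main AE analysis leaves out flagged Day 1-7 reactogenicity events that the protocol's primary AE endpoint counts, and SAP 2.1 declares no change

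*SAP*

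**What the plan says.** **Definition.** Protocol section 3 gives the primary AE estimand as "The percentage of participants reporting AEs from vaccination through 1 month after vaccination". Table 5 in Protocol 9.3.2 matches it: "All of the AEs within 1 month and SAEs/NDCMCs throughout the study will be descriptively summarized with counts, percentages". Neither has an exclusion. The variable in SAP 2.2.1.1.2 is "AEs reported within 1 month after vaccination".

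**Main analysis.** SAP 6.1.2.1 states: "The main analysis will be based on AEs and will exclude the reactogenicity events that were reported in the AE CRF (except for SAEs". The derivation is in SAP 3.1.1.3: "Variables 1 through 6 listed above will be derived from excluding any reactogenicity (but not excluding reactogenicity SAEs) reported in the AE CRF", limited to the e-diary collection period. Variable 1 is any AE within 1 month and variable 6 is any AE leading to study withdrawal.

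**Which events count as reactogenicity.** Under SAP 3.1.1 the clinical team reviews a listing of AEs from the 7 days after vaccination and flags preferred terms before database lock. Matching AEs become reactogenicity data whether or not they are judged related. If a participant transmitted no e-diary data, the CRF events are not used and the participant is left out of the reactogenicity analysis.

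**All-AE version and change control.** SAP 6.1.2.3 plans an analysis of all AEs without the exclusion, as a sensitivity analysis. SAP 2.1 says: "There is no change in analysis from the plan specified in the protocol". Protocol section 9, echoed in SAP section 2, says "any major modifications of the primary endpoint definitions or their analyses will also be reflected in a protocol amendment".

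**The concern.** The AE percentage is a primary endpoint in a study whose primary objective is to describe safety at each dose level. The figure that the SAP labels main is not the figure that the protocol defines, and the section meant to disclose such differences says there are none. A reader who takes the protocol's definition to the main AE table would read the number as the rate of all AEs.

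Relabelling an event as reactogenicity does little harm if it is then counted there. The question is whether that always happens, and whether the exclusion reaches variables that have no counterpart in the reactogenicity tables. The SAP does not list the flagged preferred terms, so the extent of the exclusion cannot be read from the documents.

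**Working it through.** **Step 1. Where each type of CRF event counts, following the text as written.**

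| Event on the AE CRF within 1 month | Protocol AE endpoint | SAP main AE analysis | SAP main reactogenicity analysis | SAP 6.1.2.3 |
|---|---|---|---|---|
| Flagged term, Days 1-7, non-serious, some e-diary data | yes | no | yes | yes |
| Flagged term, Days 1-7, non-serious, no e-diary data | yes | **no** | **no** | yes |
| Flagged term, Days 1-7, serious | yes | yes | yes, if some e-diary data | yes |
| Same term, starting after Day 7 | yes | yes | no | yes |
| Any other AE | yes | yes | no | yes |

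The second row is the gap. The main AE analysis uses the safety population, so a child with no e-diary stays in the AE denominator. If flagged events are that child's only AEs, the child is counted as having none.

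**Step 2. Size.** The documents state no AE rate, so there is no plan figure to reproduce. Group sizes are consistent: six groups of about 20 give 6 × 20 = 120, and the minimum path gives 40 + 20 = 60, matching the stated range of about 60 to 120.

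Let *A* be the participants in a group of *n* with any AE within 1 month, and *k* those whose only AEs are flagged, non-serious, Day 1-7 CRF events.

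- Protocol figure: *A/n*
- SAP main figure: (*A* − *k*)/*n*
- Difference: *k/n*, which is zero or positive

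Per such child, the difference is 1/20 = 5.0 points in an SAP reporting group. It is 1/40 = 2.5 points if the older stratum is pooled at one dose level, as in Protocol Table 5.

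Illustration with *n* = 20, **assuming** that 4 children have some other AE (Clopper-Pearson 95% intervals):

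| *k* (assumed) | SAP main | All AEs |
|---|---|---|
| 0 | 20.0% (5.7-43.7) | 20.0% (5.7-43.7) |
| 1 | 20.0% (5.7-43.7) | 25.0% (8.7-49.1) |
| 2 | 20.0% (5.7-43.7) | 30.0% (11.9-54.3) |
| 4 | 20.0% (5.7-43.7) | 40.0% (19.1-63.9) |

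If each child independently has probability *q* of being such a case, the chance that the two figures differ in a group of 20 is 1 − (1 − *q*)^20. That is 0% at *q* = 0, 33% at 0.02, 64% at 0.05 and 88% at 0.10. These values of *q* are also assumptions.

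**Step 3. Withdrawal.** Variable 6 falls under the closing rule of SAP 3.1.1.3. The reactogenicity summaries (SAP 6.1.1) cover presence, severity, duration and onset, not withdrawal. A child withdrawn for a non-serious flagged event would appear in the disposition table with a reason (SAP 6.5.2) but not in the count of AEs leading to withdrawal.

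**Step 4. Consistency within SAP 3.1.1.3.** Items 2 and 3 speak of *related* reactogenicity; the closing rule for variables 1 to 6 says *any*. In item 2 this changes nothing, since only related AEs are counted there. In item 3 (immediate AEs) it does: an unrelated flagged event within 30 minutes stays in under the item and goes out under the closing rule.

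**The case against.** The best defence is that this is classification, openly stated. Prompted reactions and AEs are separate primary endpoints. Protocol 8.3.4 says that e-diary reactions need not be entered as AEs, and Protocol 9.3.1 uses CRF reactogenicity to fill missed diary days. SAP 3.1.1 attributes the use of CRF events as reactogenicity to FDA feedback. Excluding them from the AE table avoids counting one event in two primary tables. The all-AE table is planned anyway, and with no hypothesis test the label *main* affects no formal decision. The SAP's AE estimand also cross-refers to 3.1.1.3, so it could be said to inherit the exclusion.

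Much of this stands. For children with e-diary data the events mostly move from one primary endpoint to another. But Protocol 9.3.1 only adds CRF events to reactogenicity; nowhere does the protocol remove them from the AE count. A cross-reference inside the SAP does not alter Protocol section 3 or Table 5. The argument also fails for children with no e-diary and for withdrawals.

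Four stronger readings are tempting and not supported:

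- **All non-serious reactogenicity-type AEs are dropped.** Only flagged terms in Days 1-7 are.
- **The main figure is always lower.** It equals the protocol figure when *k* = 0.
- **The primary severe and life-threatening AE rates are altered.** The exclusion does apply to those variables, but the protocol sets no such primary percentage and SAP 6.1.2.2 lists them as supplementary.
- **The amendment rule has been broken.** That rule covers major modifications, and neither document says what is major.

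**Conclusion.** The point holds. The main AE percentage in the SAP is not the primary AE percentage in the protocol, and SAP 2.1 does not disclose the difference. The figure is the same or lower, by 5 points per affected child in a group of about 20. The number of affected children is unknown, so the total shift cannot be estimated from the documents and may be zero.

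Two consequences go beyond labelling. As written, a non-serious flagged event in a child with no transmitted e-diary enters neither main primary analysis and surfaces only in the sensitivity analysis. The count of AEs leading to withdrawal also omits flagged events. The first rests on applying the closing rule of SAP 3.1.1.3 to every participant; the SAP states no exception for those without e-diary data.

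This should be corrected before analysis. It does not show that safety data are lost, since the all-AE analysis is pre-planned.

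**What to change.** **Preferred.** Make the all-AE analysis in SAP 6.1.2.3 the main analysis of the protocol's AE endpoint, and present the version without CRF reactogenicity as supplementary.

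**If the exclusion is kept.** Declare it in SAP 2.1 and the AE estimand (2.2.1.1.2), and put it in Protocol section 3 and Table 5. Limit it to participants whose CRF events are actually counted in the reactogenicity analysis, so that children with no e-diary keep their events in the AE count.

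**In either case.** Do not apply the exclusion to AEs leading to withdrawal (variable 6), and reconcile *related* in items 2 and 3 of SAP 3.1.1.3 with *any* in its closing rule.

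**Cost.** Both AE tables are already planned, so the preferred route is mainly relabelling plus a small change to the derivation of variable 6. Keeping the exclusion also means changing protocol text. The downside of the preferred route is that the headline AE rate may be slightly higher and will overlap with the reactogenicity table; a footnote can say so.

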## **6.1.2.2.** Supplementary Analysis

To support the assessment of AEs, the endpoints below, as specified in Section 3.1.1.3, will be summarized with the same analysis population using the same presentation as specified in the main analysis:

- Immediate AEs after vaccination
- Related AEs reported within 1 month after vaccination
- Severe AEs reported within 1 month after vaccination
- Life-threatening AEs reported within 1 month after vaccination
- AEs leading to study withdrawal after vaccination
- AESIs reported throughout the study

#### **6.1.2.3. Sensitivity Analysis of AEs**

In addition, a sensitivity analysis will be conducted using all AEs (not excluding the reactogenicity events reported in the AE CRF during the e-diary collection period).

## 6.2. Secondary Endpoint(s)

#### 6.2.1. RSV A- and RSV B-Neutralizing Antibody Titers

NTs will be summarized for each of the 6 age/risk/dose-level groups (Section 2.2.2.1.1).

## 6.2.1.1. Main Analysis

- Estimand strategy: Hypothetical approach (Section 2.2.2.1.1).
- Intercurrent events and missing data: All data collected after or at intercurrent events will not be included; missing data will not be imputed.
- Analysis set: Evaluable immunogenicity population (Section 4).
- Analysis timing: At primary analyses (when all primary endpoint data are available). The data will be summarized after primary analysis with all time points presented.
- Analysis methodology: 95% CIs of GMTs and GMFRs (Section 5.2.2).
- Descriptive statistics, including sample size (n), RSV A NT, RSV B NT, and RSV A/B NT GMTs and GMFRs, and 95% CIs for GMTs and GMFRs at each applicable visit, will be presented for each vaccine group (Section 5.2.2).
- RCDCs for RSV A and RSV B will be plotted 1 month after RSV vaccination, by vaccine group.

## 6.2.1.2. Supplementary Analysis

To support the assessment of immunogenicity, estimands as specified in Section 2.2.3 using the treatment policy strategy will be summarized with the mITT immunogenicity population using the same presentation as specified in the main analysis, without the RCDCs.

#### 6.2.2. **PBMCs**

#### 6.2.2.1. Main Analysis

- Estimand strategy: Hypothetical approach (Section 2.2.2.1.2).
- Intercurrent events and missing data: All data collected after or at intercurrent events will not be included; missing data will not be imputed.
- Analysis set: Evaluable immunogenicity population (Section 4).

- Analysis timing: At primary analyses if data are available at that time. If data are available after primary analysis, data will be summarized after primary analysis.
- Descriptive statistics, including sample size (n), mean (standard deviation), median, Q1, Q3, range of RSV F antigen–specific CD4+ T cells secreting IFNγ, and RSV F antigen–specific CD4+ T cells secreting IL-4 at each applicable visit, will be presented for each group (Section 5.2.2).
- Descriptive statistics, including sample size (n), mean (standard deviation), median, Q1, Q3, range of RSV F antigen–specific CD4+ T cells secreting IFNγ, and RSV F antigen–specific CD4+ T cells secreting IL-4 fold rise at each applicable visit, will be presented for each group (Section 5.2.2).

#### 6.3. Other Endpoint(s)

## 6.3.1. RSV NT Seroresponse

Descriptive statistics, including the proportion (%) of participants with RSV A NT seroresponse and RSV B NT seroresponse at 1 month after vaccination, the numerator (n) and the denominator (N) used in the proportion calculation, and the 95% CI for percentage using the Clopper-Pearson method, will be presented in the evaluable immunogenicity population.

## 6.4. Subset Analyses

Not applicable.

## 6.5. Baseline and Other Summaries and Analyses

Data will be summarized for each of the 6 age/risk/dose-level groups.

#### 6.5.1. Baseline Summaries

For each group, descriptive summary statistics for demographic characteristics (age at vaccination, sex, race, and ethnicity) and baseline information (weight, height) will be generated, as well as for all participants in total, based on the safety population. The proportions of participants prespecified as being at risk (Section 3.4.2) will also be included.

Summary data will also be presented for the evaluable immunogenicity population.

Participant data listings for demography and baseline characteristics will also be generated.

## 6.5.2. Study Conduct and Participant Disposition

The number and proportion of randomized participants will be included in the participant disposition summary. In addition, vaccinated participants who completed the 6-month follow-up visit, and who withdrew before the follow-up visit, along with the reasons for withdrawal, will be tabulated by group and for all participants. The reasons for withdrawal will be those as specified in the database.

Participants excluded from the evaluable and mITT populations will also be summarized with reasons for exclusion.

Participant study compliance such as e-diary completion, major protocol deviation, and blood draw within the protocol/analysis specified window will all be summarized.

Standard listings will all be generated, including, but not limited to, participants who withdrew during the study, participants excluded from analysis populations, and participants with major protocol violations.

#### 6.5.3. Nonstudy Vaccines

Nonstudy vaccines recorded after signing the ICD through the end of the study will be categorized according to the WHODrug Dictionary and may be summarized by vaccine group and for all participants included in the safety population.

A listing may be used to replace the table.

#### 6.6. Safety Summaries and Analyses

#### 6.6.1. Adverse Events

For all of the AEs categorized in Section 3.1.1.3, each individual AE will be categorized by MedDRA and descriptively summarized by vaccine group.

For Tier 1 events, 2-sided 95% CIs for the events will be provided.

#### 7. INTERIM ANALYSES

No interim analysis is planned.

#### 7.1. Introduction

#### 7.1.1. Analysis Timing

As this study is open-label, the sponsor may conduct reviews of the data during the course of the study for the purpose of decision making.

## 9. APPENDICES

## **Appendix 1. List of Abbreviations**

Abbreviation	Term
AE	adverse event
AESI	adverse event of special interest
BLQ	below the limit of quantitation
CAETeLiSt	Custom Adverse Event Term List System
CI	confidence interval
CRF	case report form
e-diary	electronic diary
FDA	Food and Drug Administration (United States)
GMC	geometric mean concentration
GMFR	geometric mean fold rise
GMT	geometric mean titer
ICD	informed consent document
ΙΕΝγ	interferon gamma
IL-4	interleukin 4
IRT	interactive response technology
LLOQ	lower limit of quantitation
MCAR	missing completely at random
MedDRA	Medical Dictionary for Regulatory Activities
mITT	modified intent-to-treat
N/A	not applicable
NDCMC	newly diagnosed chronic medical condition
NT	neutralizing titer
PBMC	peripheral blood mononuclear cell
PRR	patient-reported reactogenicity
PT	preferred term
Q1, Q3	first quartile, third quartile
QNS	quantity not sufficient
RCDC	reverse cumulative distribution curve
RSV	respiratory syncytial virus
RSV A	respiratory syncytial virus subgroup A
RSV B	respiratory syncytial virus subgroup B

Abbreviation	Term
RSVpreF	respiratory syncytial virus stabilized prefusion F subunit vaccine
SAE	serious adverse event
SAP	statistical analysis plan
SOC	system organ class
WHODrug	World Health Organization Drug Dictionary
Dictionary	

